### **Qualification Process for Clinical Trials**

Using the authority found in §1142 of the Act (cross-referenced in §1862(a)(1)(E) of the Act), the Agency for Healthcare Research and Quality (AHRQ) will convene a multi-agency Federal panel (the "panel") composed of representatives of the Department of Health and Human Services research agencies (National Institutes of Health (NIH), Centers for Disease Control and Prevention (CDC), the Food and Drug Administration (FDA), AHRQ, and the Office of Human Research Protection), and the research arms of the Department of Defense (DOD) and the Department of Veterans Affairs (VA) to develop qualifying criteria that will indicate a strong probability that a trial exhibits the desirable characteristics listed above. These criteria will be easily verifiable, and where possible, dichotomous. Trials that meet these qualifying criteria will receive Medicare coverage of their associated routine costs. This panel is not reviewing or approving individual trials. The multi-agency panel will meet periodically to review and evaluate the program and recommend any necessary refinements to CMS.

Clinical trials that meet the qualifying criteria will receive Medicare coverage of routine costs after the trial's lead principal investigator certifies that the trial meets the criteria. This process will require the principal investigator to enroll the trial in a Medicare clinical trials registry, currently under development.

Some clinical trials are automatically qualified to receive Medicare coverage of their routine costs because they have been deemed by AHRQ, in consultation with the other agencies

represented on the multi-agency panel to be highly likely to have the above-listed seven desirable characteristics of clinical trials. The principal investigators of these automatically qualified trials do not need to certify that the trials meet the qualifying criteria, but must enroll the trials in the Medicare clinical trials registry for administrative purposes, once the registry is established.

Effective September 19, 2000, clinical trials that are deemed to be automatically qualified are:

1. Trials funded by NIH, CDC, AHRQ, CMS, DOD, and VA;
2. Trials supported by centers or cooperative groups that are funded by the NIH, CDC, AHRQ, CMS, DOD and VA;
3. Trials conducted under an investigational new drug application (IND) reviewed by the FDA; and
4. Drug trials that are exempt from having an IND under 21 CFR 312.2(b)(1) will be deemed automatically qualified until the qualifying criteria are developed and the certification process is in place. At that time the principal investigators of these trials must certify that the trials meet the qualifying criteria in order to maintain Medicare coverage of routine costs. This certification process will only affect the future status of the trial and will not be used to retroactively change the earlier deemed status.

Medicare will cover the routine costs of qualifying trials that either have been deemed to be automatically qualified or have certified that they meet the qualifying criteria unless CMS's Chief Clinical Officer subsequently finds that a clinical trial does not meet the qualifying criteria or jeopardizes the safety or welfare of Medicare beneficiaries.

Should CMS find that a trial's principal investigator misrepresented that the trial met the necessary qualifying criteria in order to gain Medicare coverage of routine costs, Medicare

coverage of the routine costs would be denied under §1862(a)(1)(E) of the Act. In the case of such a denial, the Medicare beneficiaries enrolled in the trial would not be held liable (i.e., would be held harmless from collection) for the costs consistent with the provisions of §1879, §1842(l), or §1834(j)(4) of the Act, as applicable. Where appropriate, the billing providers would be held liable for the costs and fraud investigations of the billing providers and the trial's principal investigator may be pursued.

Medicare regulations require Medicare+Choice (M+C) organizations to follow CMS's national coverage decisions. This NCD raises special issues that require some modification of most M+C organizations' rules governing provision of items and services in and out of network. The items and services covered under this NCD are inextricably linked to the clinical trials with which they are associated and cannot be covered outside of the context of those clinical trials. M+C organizations therefore must cover these services regardless of whether they are available through in-network providers. M+C organizations may have reporting requirements when enrollees participate in clinical trials, in order to track and coordinate their members' care, but cannot require prior authorization or approval. For the initial implementation, Medicare contractors will pay providers directly on a fee for service basis for covered clinical trial services for beneficiaries enrolled in M+C plans.

## **Appendix C. Methods of Contraceptives**

The below listed methods meet the requirements for contraception as per the CTGF guidance.

If female, subject must be either postmenopausal defined as:

- Age  $\geq$  55 years with no menses for 12 or more months without an alternative medical cause.
- Age  $<$  55 years with no menses for 12 or more months without an alternative medical cause AND an FSH level  $>$  40 IU/L.

### **OR**

- Permanently surgically sterile (bilateral oophorectomy, bilateral salpingectomy or hysterectomy).

### **OR for Women of Childbearing Potential**

- Agreeing to practice ONE effective method of birth control while receiving G/P or G/P + SOF; TWO effective methods of birth control while receiving G/P + RBV, or G/P + SOF + RBV (as outlined in the subject information and consent form or other subject information documents), starting with Day 1 and for 30 days after stopping G/P (if randomized to non-RBV Arm), or G/P + SOF, or 6 months after stopping RBV (or per local RBV label).
  - Progestogen-only hormonal contraception (oral, injectable, implantable) associated with inhibition of ovulation, initiated at least 1 month prior to Study Day 1.
  - Bilateral tubal occlusion/ligation.
  - Vasectomized partner(s), provided the vasectomized partner has received medical assessment of the surgical success and is the sole sexual partner of the WOCBP trial participant.
  - Non-ethinyl estradiol hormone-releasing Intrauterine device (IUD)
  - Non-ethinyl estradiol hormone-releasing Intrauterine hormone-releasing system (IUS)
  - Male or female condom with spermicide (male and female condom must not be used together)
  - Diaphragm with spermicide
  - Cervical cap with spermicide
  - Contraceptive sponge with spermicide
  - True abstinence: Refraining from heterosexual intercourse when this is in line with the preferred and usual lifestyle of the subject (periodic abstinence] e.g., calendar, ovulation, symptothermal, post-ovulation

methods] and withdrawal are not acceptable).  
○sexually active with female partners only

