### **Definition of Terms**

Study Drug	Glecaprevir (ABT-493), pibrentasvir (ABT-530), Ribavirin (RBV), *Sofosbuvir (GS-7977)
Study Day 1	First day of study drug dosing
Treatment Period	Day 1 through last dose of study drug
Post-Treatment Period	Day after the last dose of study drug through Post-Treatment Week 12 or Post-Treatment Discontinuation

Note: Differentiation between terms within the Main Study and Re-Treatment Substudy will be made with the use of headers throughout the protocol

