8. If female, the subject must be either postmenopausal, permanently surgically sterile, or for women of childbearing potential must be willing to use protocol specified method(s) of contraception (Appendix C) and have a negative serum pregnancy test at Screening and a negative urine pregnancy test on Day 1 prior to dosing.  
If male, the subject must be surgically sterile, have a female partner who is postmenopausal or permanently sterile, or if sexually active with female partner(s) of childbearing potential, must be willing to use protocol specified method(s) of contraception (Appendix C).
9. HIV+ subjects must be on a stable, qualifying HIV-1 ART regimen for at least 8 weeks prior to Screening.  
The HIV-1 ART regimen must include at least one of the following ARV agents:
  - Raltegravir (RAL) PO BID
  - Dolutegravir (DTG) PO QD or PO BID
  - Rilpivirine (RPV) PO QD
  - Elvitegravir/cobicistat (EVG/COBI) PO QD

In addition to the above medications, subjects may take a nucleoside/nucleotide reverse transcriptase inhibitor (N(t)RTI) backbone containing any of the following:

- Tenofovir disoproxil fumarate (TDF) PO QD
- Tenofovir alafenamide (TAF) PO Q

- Abacavir (ABC) PO QD or BID
- Emtricitabine (FTC) PO QD
- Lamivudine (3TC) PO QD or BID

Subjects receiving any other HIV-1 ART in addition to those noted above would not be eligible for enrollment in the study.

Subjects on a stable ART regimen must have the following:

- Two consecutive locally obtained CD4+ count  $\geq 200$  cells/mm^3 (or CD4+ %  $\geq 14\%$ ) closest to the date of the Screening visit; and
- Two consecutive locally obtained Plasma HIV-1 RNA  $< 50$  copies/mL closest to the date of the Screening visit

10. For subjects participating in the Retreatment sub-study, must have failed treatment with G/P  $\pm$  RBV in the Main study.

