### **5.2.2                   Exclusion Criteria**

1. Female subject who is pregnant, breastfeeding, or is considering becoming pregnant during the study or for 30 days after the last dose if randomized to G/P or 6 months after the last dose if randomized to RBV (or as directed per the local RBV label).

Male subject whose partner is pregnant or planning to become pregnant during the study or for 30 days after the last dose if randomized to G/P or 7 months after the last dose if randomized to RBV (or as directed per the local RBV label).

2. HCV genotype performed during screening indicating infection with any non-GT1 HCV genotype (applicable during screening for Main Study only).
3. Requirement for and inability to safely discontinue the medications or supplements listed in **Table 4** at least 2 weeks or 10 half-lives (whichever is longer) prior to the first dose of any study drug.

4. Clinically significant abnormalities or co-morbidities, or recent (within 6 months prior to study drug administration) alcohol or drug abuse that make the subject an unsuitable candidate for this study in the opinion of the investigator.
5. Positive test result at Screening for hepatitis B co-infection (HBsAg positive or Hep B Core Ab -Total positive with detectable HBV DNA) or anti-human immunodeficiency virus antibody (HIV Ab) in a patient without known history of HIV+ and stable HART therapy (applicable during screening for Main Study only).
6. Screening laboratory analyses showing any of the following abnormal laboratory results:
  - Total bilirubin  $\geq 3.0$  mg/dL.
  - Albumin  $< 2.8$  g/dL.
  - Hemoglobin  $< 11$  g/dL for women;  $< 12$  g/dL for men, applicable only to subjects receiving RBV
7. Prior therapy with a HCV Protease Inhibitor at any time (applicable during screening for Main Study only).
8. Receipt of any investigational product within a time period equal to 10 half-lives of the product, if known, or a minimum of 6 weeks (whichever is longer) to study drug administration.
9. Consideration by the investigator, for any reason, that the subject is an unsuitable candidate to receive G/P or, if cirrhotic, RBV (applicable to Main Study only, see exclusion #12 for considerations for Retreatment sub-study).
10. History of severe, life-threatening or other significant sensitivity to any excipients of the study drugs.
11. Subjects who cannot participate in study per local law.

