## Protocol

B16-439 November 20, 2018

Activity	Screening	Day 1 a	Wk 4	Wk 8	Wk 12 or EOT	Wk 16 i EOT	Premature D/C b
REQUIRED ASSESSMENT outside of Standard of Care							
Informed Consent c	X						
Verification of Eligibility/Randomization	X j						
Hematology/Chemistry/PT/INR g	X	X	X	X	X	X	X
Pregnancy Test (serum [s] g urine [u] k ) for WOCBP only	X (s)	X (u)	X (u)	X (u)	X (u)	X (u)	X (u)
HCV Genotype and Subgenotype; HBV serologies g	X o						
HIV Ab g,l	X o						
FibroTest and APRI g,h	X o						
HCV RNA Samples g	X	X	X	X	X	X	X
HCV Resistance Sample g		X	X	X	X	X	X
Archive Plasma Sample g	X	X	X	X	X	X	X
Study Drugs Dispensed		X	X	X	X i		
Randomization Request submitted centrally at least 5 business days prior to planned Day 1	X j						
Perform Study Drug Accountability and Review of Study Drug Adherence			X	X	X	X	X
Authorization Request for Retreatment	X j						
Upload signed central lab reports evaluating clinical significance of abnormal results	X	X	X	X	X	X	X
Medical Records & Blood sample collection Verification Worksheet and Records Submission	X	X	X	X	X	X	X

Wk = Week; EOT = End of treatment; D/C = Discontinuation

- a. All procedures to be performed prior to first dose
- b. Subjects who prematurely discontinue the Treatment Period should return to the site to complete the Premature D/C Visit Procedures (preferably prior to the initiation of any

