#### **6.1.6                    Pregnancy**

Female subjects randomized or assigned to non-RBV containing regimen in Main study or Retreatment sub-study should avoid pregnancy starting with screening and through 30 days after completion of study drug. Female subjects randomized or assigned to RBV containing regimen in Main study or Retreatment sub-study should avoid pregnancy starting with Screening and through 6 months after completion of study drug (or as per

local RBV label). Male subjects randomized to G/P in Main study or receiving G/P plus SOF in Retreatment sub-study and their partners should avoid pregnancy starting with screening and through 30 days after completion of study drug. Male subjects randomized or assigned to RBV containing regimen in Main study or Retreatment sub-study and their partners should avoid pregnancy starting with Screening and through 7 months after completion of study drug (or as per local RBV label).

Pregnancy in a study subject must be reported to the sponsor within 1 working day of the site becoming aware of the pregnancy and should be reported to the Ribavirin Pregnancy Registry, as applicable. Administration of G/P in Main study or G/P plus SOF in Retreatment sub-study may be continued at the investigator's discretion after discussion with the subject, if the benefit of continuing therapy is felt to outweigh the risk (Section 5.4.1). If a subject is discontinued, the subject will be monitored for SVR in the Post-Treatment Period as described in Section 5.1.3.

Information regarding a pregnancy occurrence in a study subject and the outcome of the pregnancy will be collected for pregnancies occurring up to 30 days after the end of treatment for subjects receiving a non-RBV containing regimen or up to 6 months (female subjects) or 7 months (male subjects) after the end of treatment for subjects receiving a RBV containing regimen.

Pregnancy in a study subject is not considered an adverse event. However, the medical outcome of an elective or spontaneous abortion, stillbirth or congenital anomaly is considered a serious adverse event and must be reported to the sponsor within 24 hours of the site becoming aware of the event.

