***Male Subjects***

Subject must be surgically sterile (vasectomy with medical assessment confirming surgical success)

**OR**

Have a female partner who is postmenopausal or permanently sterile (bilateral oophorectomy, bilateral salpingectomy or hysterectomy)

**OR**

if sexually active with female partner(s) of CBP must agree to practice ONE effective method of birth control while receiving G/P, or G/P + SOF; or TWO effective methods of birth control while receiving G/P + RBV, or G/P + SOF + RBV (as outlined in the subject information and consent form or other subject information documents), starting with Day 1 and for 30 days after stopping G/P (if randomized to non-RBV Arm), or G/P + SOF; or 7 months after stopping RBV (or per local RBV label).

- Any approved and commercially available hormonal contraception for female partners
- Any approved and commercially available, including any hormone-eluting, devices for female partners of male subjects
- Male or female condom with spermicide (male and female condom must not be used together)
- Female partner using a diaphragm with spermicide
- Female partner using a cervical cap with spermicide
- Female partner using a contraceptive sponge with spermicide
- True abstinence: Refraining from heterosexual intercourse-when this is in line with the preferred and usual lifestyle of the subject. (Note: Periodic abstinence (e.g., calendar, ovulation, symptothermal, post-ovulation methods] and withdrawal are not acceptable).

sexually active with male partners only

Additionally, male subject agrees not to donate sperm from Study Day 1 through 7 months after the last dose of study drug (or as directed by the RBV prescribing information).

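### Appendix C starts required contraception on Day 1, although Section 6.1.6 asks that pregnancy be avoided from Screening; some subjects therefore have no required method before a first dose that may include ribavirin

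*Protocol*

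**What the plan says.** Inclusion Criterion 8 (Section 5.2.1) sends the reader to Appendix C for methods. A woman of childbearing potential "must be willing to use protocol specified method(s) of contraception (Appendix C) and have a negative serum pregnancy test at Screening", plus a negative urine test on Day 1 before dosing. The criterion sets no earlier start for contraception.

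Appendix C sets the period. For women of childbearing potential the duty runs "starting with Day 1 and for 30 days after stopping G/P (if randomized to non-RBV Arm), or G/P + SOF, or 6 months" after ribavirin. For men with partners of childbearing potential it runs "starting with Day 1 and for 30 days after stopping G/P (if randomized to non-RBV Arm), or G/P + SOF; or 7 months" after ribavirin. The Definition of Terms gives Study Day 1 as "First day of study drug dosing".

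Section 6.1.6 uses a different start. Women on a ribavirin regimen "should avoid pregnancy starting with Screening and through 6 months after completion of study drug". Men on such a regimen and their "partners should avoid pregnancy starting with Screening and through 7 months after completion of study drug". Non-ribavirin regimens also start at Screening and end at 30 days. The section covers both the Main study and the Retreatment sub-study, and names no method.

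The notes to Table 4 (Section 5.2.4.3) bar contraceptives containing ethinyl estradiol from 2 weeks before the first dose.

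**The concern.** The end dates in Appendix C and Section 6.1.6 agree; only the start differs. A site that follows Appendix C, the part eligibility relies on, can properly tell many subjects that no method is required until the day they take the first tablet. The Table 4 restriction sharpens this. A woman using a combined hormonal product must stop it about two weeks before dosing, and nothing obliges her to replace it until Day 1. Those are also the days in which a new conception is most likely to escape a Day 1 urine test.

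The stake is subject safety. Section 3.6 describes ribavirin as a category X teratogen, and in some parts of the trial it is in the first dose.

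**Working it through.** No formula in the protocol bears on this point, so the check is a comparison of texts with a few simple intervals.

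1. **Start and end of the duty.**

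| | Appendix C | Section 6.1.6 |
|---|---|---|
| Start, women and men | Day 1 | Screening |
| End, no ribavirin | 30 days | 30 days |
| End, ribavirin, women | 6 months | 6 months |
| End, ribavirin, men | 7 months | 7 months |

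2. **Who has no required method before Day 1.** Appendix C requires progestogen-only hormonal contraception to begin at least 1 month before Day 1, and tubal occlusion or a vasectomised partner is by nature already in place. That leaves barrier methods, an intrauterine device or system, and abstinence. It also leaves women coming off ethinyl estradiol: their product stops 14 days before first dose and the duty begins on Day 1, so 14 days have no required method.

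3. **Length of the interval.** Section 5.1.3 has records submitted at least 5 business days (about 7 calendar days) before Day 1. Beyond 45 days from Screening it requires repeat laboratory tests, and Section 5.1.3.1 allows one rescreen of subjects not enrolled by then. The usual interval is therefore roughly 7 to 45 days.

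4. **Controls within the interval.** Section 5.1.3 has eligibility assessed from Screening up to dosing on Day 1, so Exclusion Criterion 1 applies throughout. It bars a woman who is pregnant or considering pregnancy, and a "Male subject whose partner is pregnant or planning to become pregnant during the study". With the serum test at Screening and the pre-dose urine test, a known or detectable pregnancy already prevents dosing. What remains is a conception too early to detect on Day 1, or a partner pregnancy nobody knows of. That an early conception can escape a urine test is an assumption; the protocol gives no test sensitivity.

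5. **If a conception is missed.** Table 5 next tests female subjects at Week 4, so the worst case is about 4 × 7 = 28 days of ribavirin before retesting. Section 5.4.1 then stops ribavirin at once.

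6. **Where the first dose can include ribavirin.**
   - Arm C: up to 75 cirrhotic subjects randomised 1:1, 75 / 2 = 37.5, so 37 or 38. This is a ceiling, not a count at risk, because the shares who can conceive or father a child and who already use a method are not given.
   - New starts in Arms A, B or D after a ribavirin addition (Section 5.5.5), which may never happen. Subjects already on G/P have been bound by Appendix C since their own Day 1.
   - Retreatment with ribavirin, chiefly after a non-ribavirin regimen, since that duty ends 30 days after the last G/P dose. After Arm C the earlier duty probably still runs: 6 months is about 183 days, leaving 183 − 84 = 99 days at Post-Treatment Week 12 for women; for men, 213 − 84 = 129 days.

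**The case against.** The strongest reply is that the sections do not conflict. Section 6.1.6 states an aim from Screening, Appendix C states methods tied to drug exposure, and a subject can follow both. This stands as logic: the difference is one of start time, and a reader who infers a strict contradiction goes beyond the text. It does not answer the practical point that an aim without a required method is weaker than the same protocol demands from Day 1.

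Three other stronger readings are tempting but unsupported.

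- A reader might infer that nobody has a required method before first dose. The progestogen-only lead-in and the permanent methods show otherwise.
- A reader might add that partners of male subjects are never tested, since Table 5 limits pregnancy tests with the words "for WOCBP only", and that the mandatory ribavirin stop in Section 5.4.1 concerns a pregnant subject only. Both observations are accurate, but they are separate matters that a change of start date would leave untouched.
- A reader might measure the retreatment gap as 84 − 30 = 54 days, from the lapse of the Main study duty to Post-Treatment Week 12. That counts time off study drug. The relevant interval is retreatment screening to retreatment Day 1, where Section 6.1.6, Inclusion Criterion 8, Exclusion Criterion 1 and both pre-dose tests apply again.

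Finally, Appendix C refers to the consent form, which is not shown and may already say Screening. If so, the practical gap may be closed, though the protocol's two sections would still differ.

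**Conclusion.** The point holds in limited form. Appendix C begins the duty later than Section 6.1.6 implies. Following its text leaves subjects on barrier methods, intrauterine methods or abstinence without a required method before first dose, and women stopping ethinyl estradiol without a required replacement for 14 days. The residual risk is an undetectable early conception or an unknown partner pregnancy, and it matters mainly when the first dose includes ribavirin.

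Its size cannot be worked out from the protocol. Calling it small is a judgement resting on the two pre-dose tests and Exclusion Criterion 1. It assumes that sites apply both through Day 1 and that the consent text does not impose an earlier start. No endpoint, estimate or analysis changes. Because the remaining exposure would be to a teratogen, the correction is more than clerical and should be made.

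**What to change.** In both Appendix C clauses, move the start of the duty from Day 1 to Screening, or to retreatment screening for the sub-study. From then until first dose require at least one effective method free of ethinyl estradiol for female subjects, and one listed method for male subjects. Keep two methods while receiving ribavirin. Requiring one method before dosing works although the arm is not yet known at Screening. The progestogen-only lead-in can stay as it is. Align the consent text if it carries the Day 1 start.

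The cost is two wording changes and possibly a matching consent revision, with no added visit or test. The downside is slightly longer contraceptive use before dosing.
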